#### 10.3 Expectedness

The Principal Investigator will be responsible for determining whether an AE is expected or unexpected. An AE will be considered unexpected if the nature, severity, or frequency of the event is not consistent with the information previously described (sections 8.2 and 9.1). Note that the risks listed in Section 8.1 are considered expected and would not require reporting *unless* the frequency or severity is greater than expected. Events not listed in Section 8.1 but that are listed in the FDA-approved package insert, should

also be considered expected. In such cases, depending on the nature and severity of the event, an amendment may be necessary to add the risk to Section 8.1 and the consent form document.

# 10.4 Reporting Serious Adverse Events

If there is a suggestion that any research procedures have resulted in an injury to subjects, there will be immediate contact with the Principal Investigator who is listed on the first page of the informed consent documents. Any SAE, which is determined by the PI to be unexpected and at least possibly related to study intervention, will be reported to the IRB as soon as possible. The PI is responsible for notifying the FDA within required timeframes. The IDSMB will be notified in writing at the soonest possible timepoint that the event has been identified. The IRB and FDA and will include all known details regarding the nature of the SAE. Outcomes of SAEs not previously reported will be reported to the PI, IRB and FDA via a follow-up report.

Life-threatening or fatal unexpected adverse events associated with the use of the study drug or procedures must be reported to the IRB within 24 hours of discovery of the incident with subsequent follow-up submission of a detailed written report. The IDSMB and IRB will be notified by telephone or facsimile transmission of a human adverse event that is fatal or life-threatening no later than 7 calendar days after receiving the respective human adverse event information, followed by the subsequent submission of a written IND Safety Report. Serious and unexpected adverse events associated with the use of the study drug or procedures will be reported to the IRB with subsequent follow-up submission of a detailed written report in accordance with the respective policies and procedures of the IRB. A summary report of the findings will be prepared and submitted to the regulatory agencies. A written IND Safety Report (i.e., Form FDA 3500A) will be submitted to the FDA as soon as possible and, in no event, later than 15 calendar days following the investigator-sponsor's receipt of the respective adverse event information.

A summary of the SAEs that occurred during the previous year will be included in the FDA annual progress report as well as in the annual IRB continuing review.

# 11 Withdrawal of Subjects and Stopping Rules

This section outlines the criteria that specify when dosing an individual subject, cohort, or trial will be suspended.

#### 11.1 Adverse Events Requiring Discontinuation

For this study, a serious adverse event is any untoward clinical event that is thought by either the investigator or the sponsor to be related to the study and results in any of the following outcomes:

- 1. Death
- 2. A life-threatening adverse event
- 3. Inpatient hospitalization or prolongation of an existing hospitalization

- 4. A persistent or significant incapacity or substantial disruption of the ability to conduct normal life functions.
- 5. A congenital anomaly or birth defect
- 6. Important medical events that may not result in death, be life threatening, or require hospitalization may be considered serious when, based upon appropriate medical judgment, they may jeopardize the patient, or subject, and may require medical, or surgical intervention to prevent one of the serious outcomes listed above.

If clinically important and unexpected adverse experiences or clinically important study-related adverse experiences occur, they will be recorded on the adverse event case report form.

Adverse Events Reporting Timeline is documented in 10.4.

# Withdrawal of Subjects due to Adverse Events

Participants will be withdrawn if they experience a life-threatening adverse event, inpatient hospitalization or prolongation of existing hospitalization, a persistent or significant incapacity or substantial disruption of the ability to conduct normal life functions, or other important medical events that may not result in death, be life threatening, or require hospitalization may be considered serious when, based upon appropriate medical judgment, they may jeopardize the patient, or subject, and may require medical, or surgical intervention to prevent one of the serious outcomes listed above.

DSMB will review all events pertaining to participant withdrawals. An independent decision will be made regarding trial discontinuation based on risk assessment for current and future trial participants.

Withdrawn participants will be replaced at a proportion of 1:1. Procedures are as follows:

- Study personnel, investigators, and pharmacy will be informed of the need for replacement due to participant withdrawal.
- Subsequent data to be collected from the withdrawn participant will be restricted to the
  minimum amount necessary to continue to monitor safety, i.e., side effect diary including
  questions of sedation, LSD short form, dizziness, lightheadedness, bad dreams, nausea,
  vomiting, pruritus, hallucinations.

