#### 5.5 Screen Failures

Participants who are consented to participate in the third trimester of pregnancy, may be withdrawn from the study protocol before, during, or following the cesarean surgery if events arise such as to preclude them from participating in the remainder of the study. These participants will be considered "Screening Failures". The following list is non-comprehensive, but represents the most likely scenarios:

- Vaginal or non-cesarean delivery
- Development of exclusion-based criteria prior to cesarean surgery (i.e., severe preeclampsia, preterm delivery, NICU assessment likely, etc.)
- Severe complications during labor and/or delivery whereby the PI and/or patient's surgeon recommend a change in therapeutic response.

Withdrawn participants will be replaced at a proportion of 1:1. Procedures are as follows:

- Study personnel and investigators will be notified.
- Written documentation of withdrawal and reason for withdrawal will be noted per IRB protocol.
- Study personnel, investigators, and pharmacy will be informed of the need for replacement of pharmaceuticals due to participant withdrawal.
- Subsequent data to be collected from the withdrawn participant will be restricted to the minimum amount necessary to continue to monitor safety, i.e., side effect diary including questions of sedation, LSD short form, dizziness, lightheadedness, bad dreams, nausea, vomiting, pruritus, hallucinations.

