# 6.2 Study Drug Preparation and Dispensing

The study drug, ketamine, will be sourced by investigational (IDS) Pharmacy at UPMC Magee Women's Hospital. The infusions will be packaged and labeled for use in the clinical research study per pharmacy protocols and guidelines. Ketamine will be prepared by pharmacy with dosing instructions. There will be no blinding.

For on-site preparation and dispensing of the study drugs, the following procedures will be followed. The pharmacist of record will: maintain adequate records confirming receipt, expiration dates, or other disposition information on the investigational drug; they will record the name of the individual to whom the drug is shipped, date, quantity, and batch number. They will secure the drug in a locked storage area and monitor to ensure proper storage conditions; they will also complete regular inventory to assure accurate indication of stock on hand, as well as proper recording of stock received, dispensed, and returned. For the patients enrolled for open label pharmacokinetic studies, the pharmacist will generate a label prior to dispensing the study drug, including the date dispensed, quantity and expiration information, drug strength and dose; they will affix the label to the dispensed drug. For dispensing and drug disposition recording, they will record the date dispensed, patient initials or other identifiers, drug treatments, quantity dispensed, initials of dispenser, date and amount of patient returns documented in study records (i.e., returned drug that cannot be re-dispensed). Filing and all drug documentation will occur within study records, medical records, and logs.

Following the cesarean delivery, the initial drug administration (via IV infusion) will begin 15 minutes (± 30 minutes) after cord clamping and declaration of clinical/ hemodynamic stability by the case anesthesiologist after delivery. The maintenance dose will start 60 min (range: +15min) after the initial loading dose. The infusion will be completely stopped 12 hours after the start of infusion. The same infusion pump will follow the patient throughout the postoperative period for 12 hours until completion of the study drug. No manipulation of the infusion pump will occur by the patient. Adjustments to the rate will be at the discretion of the study team and can be physically made by study personnel qualified and trained in these procedures, or by clinical care providers under direct orders from the study team.

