### 7.5 Safety Assessments/Procedures After Ketamine Infusion Stop

Maternal side effect monitoring following the infusion will continue at 4-hour intervals for 12-hours after the cessation of ketamine infusion. Monitoring will occur via clinical staff monitoring and via patient self-report indices of side effect symptomology (Figure 1; section 1.1).

After the study drug infusion is complete, safety and efficacy assessments consist of the following. Digital diaries will assess self-reported side effects according to the study schematic Figure 1; 1.1, until 12 hours after infusion discontinuation. Vital signs will be monitored during that same period.

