#### 10.1 Severity

The severity of adverse changes in physical signs or symptoms will be classified as follows:

- *Grade 1 (Mild):* asymptomatic or mild symptoms; clinical or diagnostic observation only; intervention not indicated.
  - e.g., sedation, dizziness, lightheadedness, bad dreams, hallucinations, euphoria, dysphoria, nausea, vomiting
- *Grade 2 (Moderate):* minimal, local, or noninvasive intervention indicated; limiting ageappropriate ADL.
  - o e.g., dysphoria, vomiting
- *Grade 3 (Severe):* medically significant but not immediately life-threatening; hospitalization or prolongation of hospitalization indicated; disabling; limiting self-care/ADL.
  - o e.g., hypertensive urgency or emergency requiring escalated or inpatient treatment
- *Grade 4 (Life-threatening):* consequences; urgent intervention indicated.
  - o e.g., stroke from uncorrected severe hypertension

• *Grade 5 (Death):* event is a direct cause of death.

An independent DSMB will define frequency of monitoring of the tolerability and DLT data.

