# 11.2 Other Criteria Requiring Discontinuation

Withdrawal of Subjects for reasons other than Non-compliance or Adverse Events:

- Protocol non-adherence: incorrect dosing strategy or other non-adherence points at the judgement of the PI
- Incomplete side effect diary data, defined as missing 20% or more responses

Withdrawn participants will be replaced at a proportion of 1:1. Procedures are as follows:

• Study personnel, investigators, DSMB will be informed of the need for replacement due to participant withdrawal.

Subsequent data to be collected from the withdrawn participant will be restricted to the
minimum amount necessary to continue to monitor safety, i.e., side effect diary including
questions of sedation, LSD short form, dizziness, lightheadedness, bad dreams, nausea,
vomiting, pruritus, hallucinations.

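### Withdrawn patients are replaced 1:1 with no exception for a dosed patient who already had a DLT; a DLT replaced uncounted moves the dose decision toward escalation or leaves it unchanged

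*Combined protocol and SAP*

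**What the plan says.** Three sections withdraw patients and replace them one for one.

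- **Section 11.1** (adverse events): "Participants will be withdrawn if they experience a life-threatening adverse event, inpatient hospitalization or prolongation of existing hospitalization", with lasting incapacity and other important medical events also listed. It continues: "Withdrawn participants will be replaced at a proportion of 1:1". On data it says "Subsequent data to be collected from the withdrawn participant will be restricted to the" minimum needed for safety, and names only diary items such as sedation, nausea and hallucinations.
- **Section 11.2** (other reasons) withdraws for non-adherence, including incorrect dosing, and for "Incomplete side effect diary data, defined as missing 20% or more responses". The replacement rule and data restriction are the same.
- **Section 5.5** (screening failures) allows withdrawal "before, during, or following the cesarean surgery if events arise", again with 1:1 replacement and restricted data. Under Section 6.2, "the initial drug administration (via IV infusion) will begin 15 minutes" (± 30 minutes) after cord clamping and declared stability, so a withdrawal after surgery can be a withdrawal after dosing.

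Section 3.4.1 defines a DLT as a persisting systolic pressure or heart rate outside set limits, or complete cessation of the infusion for side effects the patient rates intolerable. It assesses the outcome for 24 hours from infusion start and stops escalation at 2 DLTs in a cohort of 3 to 6. Section 12 defines no evaluable population and has no rule for replaced patients.

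**The concern.** In a 3+3 design one patient can decide between stopping, adding three patients and escalating. Replacement is harmless when the patient's DLT status is unknown for reasons unrelated to toxicity. It is not harmless when the patient has already had a DLT and a new patient takes the place: if the first outcome is then left out, the DLT rate at that dose is understated.

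The main exposure is a DLT that also meets a serious outcome in Section 11.1. The protocol's own Grade 3 example in Section 10.1, "hypertensive urgency or emergency requiring escalated or inpatient treatment", could be one if systolic pressure stays above 160. These are the most serious toxicities in the trial. A secondary case is a patient with a known DLT who also misses 20% or more of diary responses. Appendix 2 lists 10 diary times, so if responses means whole diaries (an assumption), two missed diaries are enough. The MTD is the only primary endpoint.

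**Working it through.** **Rule used.** Stop at 2 DLTs in 3 to 6 (Section 3.4.1). Three more patients enter at 1/3, as in a traditional 3+3; Section 4 names that option. The plan's limit reproduces: 2/6 = 33.3%, its ≥33% boundary. The plan gives no DLT rate by dose and no operating characteristics, so the true rates p = 40% and 50% (both above the limit) are assumptions. Write q = 1 − p.

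**Direction.** One uncounted DLT with a DLT-free replacement turns 2/3 (stop) into 1/3 (three more patients), or 2/6 (stop) into 1/6 = 16.7% (escalate). All nine-patient outcome sequences at one dose were enumerated with every possible subset of DLTs dropped. Of 18,512 evaluable combinations, 2,149 moved from stop to escalate and none the other way. These counts show direction, not probability.

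**Chance that a level passes, all DLTs counted.** P = q³ + 3pq⁵.
- p = 0.40: 0.216 + 0.093 = 0.309
- p = 0.50: 0.125 + 0.047 = 0.172

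**If a share f of DLT patients is replaced uncounted.** The counted rate becomes p′ = p(1 − f)/(1 − pf), which goes into the same formula. The documents do not give f.

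| f (assumed) | p = 0.40: p′ | P(pass) | p = 0.50: p′ | P(pass) |
|---|---|---|---|---|
| 0 | 0.400 | 0.309 | 0.500 | 0.172 |
| 5% | 0.388 | 0.330 | 0.487 | 0.187 |
| 10% | 0.375 | 0.351 | 0.474 | 0.203 |
| 25% | 0.333 | 0.428 | 0.429 | 0.265 |

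If replacement is unrelated to DLT status, P(pass) stays at 0.309 and 0.172.

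**Effect of one uncounted DLT, replacement at the same risk.** Stops on exactly two DLTs arise as 2/3, with probability 3p²q, or as 2/6, with probability (3pq²)². A 2/3 stop becomes a pass only if the replacement is DLT-free and the next three are too (q⁴). A 2/6 stop becomes a pass if the replacement is DLT-free (q). Stops on three or more DLTs are taken as unchanged.
- p = 0.40: 0.288 × 0.1296 + 0.187 × 0.60 = 0.037 + 0.112 = 0.149. All stops are 1 − 0.309 = 0.691. Ratio 0.149/0.691 = 22%.
- p = 0.50: 0.375 × 0.0625 + 0.141 × 0.50 = 0.023 + 0.070 = 0.094. All stops are 0.828. Ratio 0.094/0.828 = 11%.

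**Vital signs after withdrawal.** Section 7.5 covers the 12 hours after the infusion stops: "Vital signs will be monitored during that same period". Section 10 follows adverse events to resolution, and Appendix 2 footnote b collects vital signs at any adverse event up to 24 hours. None of the three says that it overrides the data restriction once a patient is withdrawn.

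**The case against.** The strongest reply is that the protocol already keeps the DLT. Section 3.4.1 classifies it when the conditions are met, with no exception for withdrawal, and Table 1 marks the event as a DLT when the infusion is stopped. The restriction in Sections 11.1 and 11.2 concerns later data only. The Section 1 requirement of complete primary outcome data is met once a DLT is known. This stands as the better reading, but none of these places says whether a replaced patient stays in the count. Figure 2 may hold a counting rule, so absence can be asserted only for the visible text.

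It is also fair that the exposure is narrow. Stopping the infusion under Table 1 is not study withdrawal, and most side-effect DLTs would not meet a Section 11.1 outcome. Section 5.5's listed examples normally precede dosing. No document links missed diaries to DLTs. A DLT after a dosing error is not clean evidence about the planned dose, so leaving it out of that level is not necessarily an upward error. All of this stands and limits both the claim and the remedy. DSMB review of withdrawals protects patients but sets no counting rule.

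Two stronger readings are tempting. Because Section 12.3 calls the hemodynamic event a serious adverse event and Section 8.1 sends it to an SAE log, a reader might infer that every hemodynamic DLT is withdrawn and replaced. The documents do not support that: Section 3.4.1 calls the same event an adverse event, Section 8.1 rates such effects mild to moderate, and Section 11.1 ties withdrawal to listed outcomes. A reader might also note that 69% of stops at a true rate of 40% (0.475/0.691), and 62% at 50% (0.516/0.828), rest on exactly two DLTs, and infer that one lost DLT would raise the MTD that often. But a 2/3 stop that becomes 1/3 only adds three patients; the shares that become a pass are 22% and 11%.

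**Conclusion.** The concern holds as a conditional one. Replacement is unqualified in all three sections, and the visible text never says that a replaced patient with a DLT remains in the cohort. The plan does not say that such a DLT is dropped, and a reader should not infer that it does, nor that the MTD must rise. If it is dropped, the dose decision moves toward escalation or does not change.

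The overall size is unknown because the share of DLTs that coincide with a withdrawal reason is not given. At an assumed 5% to 10%, the chance of passing a level that is too toxic rises by 2 to 4 percentage points; at 25% it rises by 12 points at a true rate of 40% and 9 at 50%. For a single uncounted DLT with a same-risk replacement, about 22% of stops become a pass at a true rate of 40% and about 11% at 50%, through stops on exactly two DLTs. The ambiguity should be removed because it touches the only primary endpoint, bears most on the most serious toxicities, and is cheap to settle.

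**What to change.** - **Counting rule (Sections 3.4.1, 11.1, 11.2 and 12.3).** A patient dosed at the assigned level who meets the DLT definition within 24 hours of infusion start stays in that level's numerator and denominator, whether or not withdrawn, and is not replaced.
- **Replacement.** Among dosed patients, replace only those without a DLT whose DLT status cannot be determined. Do not replace for missing diaries alone when DLT status is known.
- **Dosing errors.** Report a DLT after a dosing error with the dose actually received and have the DSMB review it, rather than assigning it automatically to the planned level.
- **Data after withdrawal.** Add blood pressure and heart rate to 24 hours from infusion start.
- **Section 5.5.** Limit screening failure to withdrawal before the first dose.
- **Reporting.** List replaced patients by dose level, reason and DLT status.

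If Figure 2 already holds such a rule, repeat it in the text. Separately, Sections 3.4.1, 8.1, 11.1 and 12.3 disagree on whether a hemodynamic event is a serious adverse event and must be reconciled.

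The cost is protocol wording plus vital signs to 24 hours in the few withdrawn patients. The downside is that escalation may stop sooner and some patients with partly missing diaries stay in the analysis.

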#### 7.6 Safety Assessments/Procedures During Postpartum Surveys

Efficacy assessments, exploratory in nature, will consist of pain and depression symptom screening at regular intervals from one week postpartum until 12 weeks after delivery, according to the time intervals indicated in the study schematic Figure 1; 1.1. Positive screens for depression will be initiate an immediate response to the study team. The protocol for positive depression screens is presented in Appendix 4. All patients who screen positive for depression (EPDS total score > 14 or positive answer to question #10) will be contacted and receive consultation instructions.

After all study procedures are complete 12 weeks after delivery, there will be no further active assessments of safety and efficacy by study staff. Participants will continue to have access to their primary care physicians and emergency services.

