#### 8.3 Potential Benefits

The potential direct benefits to subject participation in this study is enhanced pain control, opioid reduction, closer follow-up for depression symptoms, and reduced depression risk. There are societal benefits in that there will be increased knowledge about the use of ketamine after birth to reduce depression, alleviate pain and decrease opioid use. Ultimately, the results of this study, if significant, will enable health care providers to improve the health of mothers.

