# 12.4 Analysis of Secondary Endpoints

Side effect acceptability ratings will be reported for each side effect reported as numbers and percentages. Examination of patient pain and depression scores in the 12-weeks post cesarean delivery will be explored. The limited sample size of the MTD design precludes definitive conclusions regarding pain and depression. General linear mixed models will be used to assess trends in pain and depression over the peripartum period according to dose exposure. Paired t-tests may be used to assess changes in pain or depression scores from the preterm to postpartum 12-week assessments.

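### The withdrawal rules keep only side effect diary items, so a dosed patient withdrawn around the infusion loses the weekly EPDS safety screen and pain surveys

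*Combined protocol and SAP*

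**What the plan says.** Three places in the protocol provide for withdrawal by the investigator:

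- **Section 5.5** covers events arising before, during or after the cesarean, so it can include a patient whose infusion has begun.
- **Section 11.1** covers serious-type adverse events: "Participants will be withdrawn if they experience a life-threatening adverse event, inpatient hospitalization or prolongation of existing hospitalization", then incapacity and other important medical events.
- **Section 11.2** covers protocol non-adherence and "Incomplete side effect diary data, defined as missing 20% or more responses".

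All three then apply the same data rule. In section 11.1 it opens "Subsequent data to be collected from the withdrawn participant will be restricted to the". The limit is set at what safety monitoring needs, and the text equates that with the diary items: the LSD short form and questions on sedation, dizziness, lightheadedness, nausea, vomiting, itching, bad dreams and hallucinations. The EPDS, pain intensity, pain unpleasantness, PROMIS-PI, PSS and SF-MPQ are not listed. All three sections also provide for replacement: "Withdrawn participants will be replaced at a proportion of 1:1".

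The weekly surveys have two uses elsewhere. Section 7.6, whose title places it among the safety assessments, says: "All patients who screen positive for depression (EPDS total score > 14 or positive answer to question #10) will be contacted". Section 12.4 says: "General linear mixed models will be used to assess trends in pain and depression over the peripartum period according to dose exposure", and allows paired comparisons to week 12. Section 8.3 names "closer follow-up for depression symptoms" among the direct benefits of taking part.

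**The concern.** The protocol does not separate leaving the infusion or the dose-finding data set from leaving follow-up. A serious event, a dosing deviation or an incomplete diary may each be a reason to exclude a patient from some analysis. None of them is a reason to stop sending her a weekly questionnaire.

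The main loss is the depression and self-harm screen. The protocol uses the EPDS as a safety instrument but leaves it out of its own safety minimum. By section 5.4, patients who enter because ketamine is part of their clinical care typically include women with a history of anxiety, depression, trauma or substance use disorder, so the screen matters in this population.

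The lesser loss is analytic. A patient withdrawn on the day of surgery gives baseline scores and nothing after, and section 12.4 has no provision for her. Where the withdrawal follows a serious event, the missing follow-up is linked to toxicity.

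**Working it through.** The plan states no figure on this point, so there is none to reproduce. The check sets the rules against the schedule, then sizes the diary route.

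**Step 1: what survives a withdrawal.**

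- Kept: diary items only (5.5, 11.1, 11.2).
- End of diary: 12 hours after the infusion stops (7.5), which is hour 24 in Appendix 2.
- Weekly surveys: Day 7 to Day 84, 12 visits (Appendix 3).
- Overlap between the two: none. No section retains the EPDS, the pain surveys or the 7.6 response for a withdrawn patient.

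A patient withdrawn around the infusion therefore has 0 of 12 weekly surveys.

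**Step 2: who is withdrawn for toxicity.** In Table 1 (section 6.3) the last step for sedation, low respiratory rate, unacceptable side effects, nausea or vomiting, or unresolved hemodynamic effects is to stop the infusion, keep monitoring under 7.4 and 7.5, and count a DLT. No text removes that patient from Appendix 3. Only the serious-type events in 11.1 do so.

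**Step 3: how many missed prompts meet the diary rule.** The section 7 text on acceptability ratings gives 15, 30 and 60 minutes and then every 4 hours to hour 24, which is 9 prompts. Appendix 2 adds hour 10, which makes 10. If responses means prompts:

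- one miss: 1/9 = 11.1% or 1/10 = 10.0%, below 20%;
- two misses: 2/9 = 22.2% or 2/10 = 20.0%, at or above 20%.

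**Step 4: chance of reaching it.** The documents give no miss rate. For an assumed rate m per prompt, with independent misses, P(at least 2 of n) = 1 − (1−m)^n − n·m·(1−m)^(n−1). For example, with n = 10 and m = 0.10: 1 − 0.349 − 0.387 = 0.264.

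| Assumed m | n = 9 | n = 10 | Expected among 12 patients |
|---|---|---|---|
| 2% | 1.3% | 1.6% | 0.2 |
| 5% | 7.1% | 8.6% | 0.9 to 1.0 |
| 10% | 22.5% | 26.4% | 2.7 to 3.2 |
| 20% | 56.4% | 62.4% | 6.8 to 7.5 |

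**Step 5: share of surveys lost.** With 1:1 replacement, w withdrawals around the infusion lose 12w of 12(N + w) scheduled surveys. For w = 1 that is 12/156 = 7.7% at N = 12, and 12/84 = 14.3% at N = 6.

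**The case against.** The best defence is that no sentence says the weekly surveys stop. The governing idea is whatever is needed to monitor safety, and 7.6 is itself a safety section. The protocol also uses "i.e." loosely: in 5.5 it introduces a list that ends in "etc.". Section 10 follows every adverse event to resolution, and 10.4 requires follow-up reports on serious events, so a strictly closed list sits badly with other text. This stands to the extent that the stop is an implication. But staff who apply the list as printed would stop the surveys, and nothing tells them to continue.

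Four stronger readings are tempting, and the documents do not support them.

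- A reader might infer that the 12.4 results would describe mainly women who tolerated the drug. Step 2 rules this out: women with a DLT stay in follow-up unless a withdrawal trigger also applies. That drowsy or unwell patients miss more prompts is plausible but not stated.
- A reader might infer that an unrelated readmission weeks later ends the surveys, because the hospitalization trigger carries no time limit. Section 11 is introduced as being about suspending dosing, 11.1 opens by defining its events as study-related, and scheduled adverse event assessment ends 12 hours after the infusion (section 10). That reading is strained.
- A reader might suppose that diary incompleteness shows only near hour 24. Misses at 15 and 30 minutes already meet the threshold.
- A reader might take the upper rows of the table as forecasts. These are monitored inpatients, prompts coincide with RASS and nursing assessments, and Appendix 4 pays $50 per listed diary time. Nothing in the protocol points to a 20% miss rate, and responses could mean items rather than prompts.

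The analytic effect is also limited: 3.3.3 makes pain and depression exploratory (3.4.2 lists them as secondary endpoints), and 12.4 already disclaims definitive conclusions.

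**Conclusion.** The point holds as a gap in the withdrawal rules. Read as written, sections 5.5, 11.1 and 11.2 take a dosed patient withdrawn around the infusion out of all 12 weekly surveys and out of the depression response in 7.6. This conflicts with the safety role that 7.6 gives the EPDS and with the benefit offered in 8.3.

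The serious-event route is narrow. The two-miss threshold on the diary route assumes that responses means prompts. The probabilities also assume independent misses at hypothetical rates, so they show sensitivity and predict nothing. The lost safety screen is the main consequence, and the effect on the exploratory models is secondary. The documents do not say whether routine care would replace the screen. The change should be made, since it is cheap and protects patients already exposed to the drug.

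**What to change.** - In 5.5, 11.1 and 11.2, state that any patient who received ketamine continues the Appendix 3 weekly surveys and the 7.6 EPDS response to week 12, unless she withdraws consent.
- In 11.2, handle incomplete diary data as missing data for the acceptability endpoint and not as a reason to end follow-up. State whether responses are counted as prompts or items, and reconcile the 9-prompt and 10-prompt schedules.
- In 12.4, include all dosed patients in the summaries and models, and report withdrawals by dose and reason.

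The cost is protocol wording, a check of the consent form, and up to 12 × $25 = $300 per retained patient in survey payments that Appendix 4 already schedules. No assessment or staff is added, and no dosing or treatment rule changes.
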